8.10.14. Follow-up of AEs and SAEs

After the initial AE/SAE report, the investigator is required to proactively follow each participant at subsequent visits/contacts.

All AEs, SAEs, and AESIs will be treated as medically appropriate and followed until resolution, stabilization, the event is otherwise explained, the participant is LTFU ([Section 7.2](#)), or the participant withdraws consent ([Section 7.1](#)).

8.10.15. Regulatory Reporting Requirements for SAEs

Prompt notification by the investigator to the Sponsor of an SAE is essential so that legal obligations and ethical responsibilities towards the safety of participants and the safety of a study intervention under clinical investigation are met.

The Sponsor has a legal responsibility to notify both the local regulatory authority and other regulatory agencies about the safety of a study intervention under clinical investigation. The Sponsor will comply with country-specific regulatory requirements relating to safety reporting to the regulatory authority, IECs, and investigators.

Investigator safety reports must be prepared for suspected unexpected serious adverse reactions according to local regulatory requirements and Sponsor policy and forwarded to investigators as necessary.

For the mRNA-1273-P305 study, events of anaphylaxis, myocarditis and pericarditis that are assessed as serious and related by the Investigator will be reported in an expedited manner to the local regulatory authority by the Sponsor, and mRNA-1273-P305 study IECs and Investigators will be notified, if appropriate according to local requirements.

An investigator who receives an investigator safety report describing an SAE or other specific safety information (eg, summary or listing of SAEs) from the Sponsor, will review and then file it along with the IB and will notify the IEC, if appropriate according to local requirements.

8.11. Safety Oversight

Safety monitoring for this study will include the blinded study team members, inclusive of at a minimum, the Sponsor medical monitor and CRO medical monitor, as well as safety reviews by an unblinded Data and Safety Monitoring Board (DSMB). The study team will conduct ongoing blinded safety reviews during the study and will be responsible for notifying the DSMB of potential safety signal events. The DSMB, composed of external, independent subject matter experts, including an unblinded statistician, will conduct unblinded reviews of safety data on a periodic basis, as defined in a DSMB charter, or as otherwise requested by the study team.

An independent CEAC comprised of medically qualified personnel, including cardiologists, will review suspected cases of myocarditis, pericarditis, and myopericarditis to determine if they meet CDC criteria for “probable” or “confirmed” events (Gargano et al 2021) and provide the assessment to the Sponsor. The CEAC members will be blinded to study vaccine assignment.

Details regarding the CEAC composition, responsibilities, procedures, and frequency of data review will be defined in the CEAC charter.

8.12. Treatment of Overdose

As the study treatment is to be administered by a healthcare professional, it is unlikely that an overdose will occur. Dose deviations will be tracked as protocol deviations ([Section 11.1.8](#)).

8.13. Pharmacokinetics

Pharmacokinetic parameters are not evaluated in this study.

8.14. Pharmacodynamics

Pharmacodynamic parameters are not evaluated in this study.

8.15. Biomarkers

Biomarker assessments (to be determined) will be evaluated as part of the study.

9. STATISTICAL ANALYSIS PLAN

This section summarizes the planned statistical analysis strategy and procedures for the study focusing on the randomized, blinded phase (Phase A) of the study. The details of statistical analysis will be provided in the statistical analysis plan (SAP), which will be finalized before the clinical database lock for the study. If changes are made to primary and/or secondary objectives or the related statistical methods after the study has begun, then the protocol will be amended (consistent with ICH Guideline E9). Changes to other secondary or exploratory analyses made after the protocol has been finalized, along with an explanation as to when and why they occurred, will be listed in the SAP or clinical study report (CSR) for the study. Ad hoc exploratory analyses, if any, will be clearly identified in the CSR. Statistical analyses of the open-label, observational phase (Phase B) will be provided in the SAP.

9.1. Blinding and Responsibility for Analyses

Phase A of this study is observer-blind. The study participants, investigators, site personnel, site monitors, and Sponsor personnel (or its designees) will be blinded to the IP administered until the unblinding occurs ([Section 6.3.7](#)) or until study database is locked and unblinded, with the following exceptions:

- An independent unblinded statistical and programming team who are not involved in study design and conduct of the CRO will perform the planned primary analysis, ([Section 9.7](#)). Select Sponsor team members including biostatistician and statistical programmers will be prespecified to be unblinded to the primary analysis results and will not communicate the results to the blinded investigators, clinic staff, clinical monitors, or participants. The details will be included in the Data Blinding Plan.
- The DSMB may review data, as appropriate, to safeguard the interests of clinical study participants and to help ensure the integrity of the study.

Procedures for breaking the blind in the case of a medical necessity are provided in [Section 6.3.7](#).

9.2. Statistical Hypotheses

Part 1:

The primary objective on immune response in Part 1 of this study is based on the participants who will receive the 4th dose in Part 1 of the study.

Primary Hypotheses:

- 1) mRNA-1273.529, as a single booster dose, is non-inferior to mRNA-1273 based on GMT ratio against the B.1.1.529 strain with a non-inferiority margin of 1.5 at Day 29.

- 2) mRNA-1273.529, as a single booster dose, is non-inferior to mRNA-1273 based on GMT ratio against the B.1.1.529 strain with a non-inferiority margin of 1.5 at Month 3.

Key Secondary Hypothesis:

mRNA-1273.529, as a single booster dose, is superior to mRNA-1273 based on GMT ratio against the B.1.1.529 strain at Day 29 or Month 3.

For the primary objective of immune response, hypotheses testing based on participants receiving the 4th dose, alpha of 0.05 (2-sided) will be allocated to the 2 time points: alpha of 0.01 (2-sided) will be allocated to Day 29, alpha of 0.04 (2-sided) will be allocated to Month 3.

The non-inferiority of mRNA-1273.529 as compared to mRNA-1273 against the B.1.1.529 strain at Day 29 will be assessed using a non-inferiority margin of 1.5 at 2-sided alpha of 0.01. The primary immunogenicity objective is considered met if non-inferiority against the B.1.1.529 strain is demonstrated, ie, the lower bound of the 99% confidence interval (CI) of the GMT ratio of mRNA-1273.529 vs. mRNA-1273 against B.1.1.529 is ≥ 0.67 (1/1.5).

The non-inferiority of mRNA-1273.529 as compared to mRNA-1273 against the B.1.1.529 strain at Month 3 will be assessed using a non-inferiority margin of 1.5 at 2-sided alpha of 0.04. The primary immunogenicity objective is considered met if non-inferiority against the B.1.1.529 strain is demonstrated, ie, the lower bound of the 96% confidence interval (CI) of the GMT ratio of mRNA-1273.529 vs. mRNA-1273 against B.1.1.529 is ≥ 0.67 (1/1.5).

Part 2:

[figure not shown]
The primary objective on immune response in Part 2 of this study is based on the participants who will receive the 4th dose in Part 2 of the study. There are 6 hypotheses on immune response of mRNA-1273.214 listed below. Part 2 of this study is considered to have met its primary objective if non-inferiority of mRNA-1273.214 against the B.1.1.529 strain, non-inferiority of mRNA-1273.214 against the prototype strain, and superiority of mRNA-1273.214 against the B.1.1.529 strain are demonstrated as compared to mRNA-1273 at Day 29 or Month 3. [Figure 2](#) depicts the hypotheses testing strategy.

Primary Hypotheses:

- 1) mRNA-1273.214, as a single booster dose, is non-inferior to mRNA-1273 based on GMT ratio against the B.1.1.529 strain with a non-inferiority margin of 1.5 at Day 29.
- 2) mRNA-1273.214, as a single booster dose, is non-inferior to mRNA-1273 based on GMT ratio against the prototype strain with a non-inferiority margin of 1.5 at Day 29.

- 3) mRNA-1273.214, as a single booster dose, is superior to mRNA-1273 based on GMT ratio against the B.1.1.529 strain at Day 29.
- 4) mRNA-1273.214, as a single booster dose, is non-inferior to mRNA-1273 based on GMT ratio against the B.1.1.529 strain with a non-inferiority margin of 1.5 at Month 3.
- 5) mRNA 1273.214, as a single booster dose, is non-inferior to mRNA -1273 based on GMT ratio against the prototype strain with a non-inferiority margin of 1.5 at Month 3.
- 6) mRNA-1273.214, as a single booster dose, is superior to mRNA-1273 based on GMT ratio against the B.1.1.529 strain at Month 3.

Figure 2: Statistical Hypothesis Testing Strategy of mRNA-1273 vs. mRNA-1273 (Part 2)

Abbreviations: M = month; mRNA = messenger ribonucleic acid.

For the primary objective of immune response, hypothesis testing based on participants receiving the 4th dose, alpha of 0.05 (2-sided) will be allocated to the 2 timepoints: alpha of 0.01 (2-sided) will be allocated to Day 29, and alpha of 0.04 (2-sided) will be allocated to Month 3.

For the primary immunogenicity objective, the non-inferiority of mRNA-1273.214 as compared to mRNA-1273 against the B.1.1.529 strain and the non-inferiority of mRNA-1273.214 as compared to mRNA-1273 against the prototype strain at Day 29 will be assessed using a non-

inferiority margin of 1.5 at 2-sided alpha of 0.01. The primary immunogenicity objective is considered met if non-inferiority against the B.1.1.529 strain and the prototype strain are both demonstrated, ie, the lower bound of the 99% confidence interval (CI) of the GMT ratio of mRNA-1273.214 vs. mRNA-1273 against B.1.1.529 is ≥ 0.67 (1/1.5) and the lower bound of the 99% CI of the GMR of mRNA-1273.214 vs mRNA-1273 against prototype is ≥ 0.67 .

Superiority of mRNA-1273.214 as compared to mRNA-1273 against the B.1.1.529 strain will be evaluated at Day 29. Once the non-inferiority of mRNA-1273.214 as compared to mRNA-1273 against the B.1.1.529 strain and against the prototype strain is demonstrated, the 99% CI of GMT ratio (mRNA-1273.214 vs. mRNA-1273) will be used to assess superiority of mRNA-1273.214 as compared to mRNA-1273. If the lower bound of the GMT ratio rules out ($>$) 1 at Day 29, superiority of mRNA-1273.214 compared to mRNA-1273 against B.1.1.529 will be considered demonstrated.

Hypotheses testing at Month 3 will be performed in the same manner, first testing 2 non-inferiority hypotheses (one against the B.1.1.529 strain and one against the prototype strain) at alpha of 0.04 level (2-sided). Once non-inferiority is demonstrated for both B.1.1.529 and prototype strains, then superiority testing against the B.1.1.529 at alpha of 0.04 level (2-sided) will be performed.

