For the primary immunogenicity objective, the non-inferiority of mRNA-1273.214 as compared to mRNA-1273 against the B.1.1.529 strain and the non-inferiority of mRNA-1273.214 as compared to mRNA-1273 against the prototype strain at Day 29 will be assessed using a non-inferiority margin of 1.5 at 2-sided alpha of 0.01. Non-inferiority against the B.1.1.529 strain and the prototype strain are both demonstrated if the lower bound of the 99% confidence interval (CI) of the GMR of mRNA-1273.214 vs. mRNA-1273 against B.1.1.529 is ≥ 0.67 (1/1.5) and the lower bound of the 99% CI of the GMR of mRNA-1273.214 vs mRNA-1273 against prototype is ≥ 0.67 .

Superiority of mRNA-1273.214 as compared to mRNA-1273 against the B.1.1.529 strain will be evaluated at Day 29. Once the non-inferiority of mRNA-1273.214 as compared to mRNA-1273 against both the B.1.1.529 and the prototype strain at Day 29 is demonstrated,

the 99% CI of GMR (mRNA-1273.214 vs. mRNA-1273) will be used to assess superiority of mRNA-1273.214 as compared to mRNA-1273. If the lower bound of the GMR rules out (>) 1 at Day 29, superiority of mRNA-1273.214 compared to mRNA-1273 against B.1.1.529 will be considered demonstrated.

Hypotheses testing at Month 3 will be performed in the same manner, first testing two non-inferiority hypotheses (one against the B.1.1.529 strain and one against the prototype strain) at alpha of 0.04 level (2-sided). Once non-inferiority is demonstrated for both B.1.1.529 and prototype strains, then superiority testing against the B.1.1.529 at alpha of 0.04 level (2-sided) will be performed.

Sample Size Justification:

This study will include:

1. Participants who received 2 doses of a COVID-19 vaccine as the primary series and the 3rd dose of a COVID-19 vaccine and will receive the 4th dose as part of the study.
2. Participants who received 2 doses of a COVID-19 vaccine as the primary series and will receive the 3rd dose as part of the study.

Part 1 (50 µg mRNA-1273.529 and 50 µg mRNA-1273 in 1:1 randomization)

The primary immunogenicity objective is to assess immune response of mRNA-1273.529 against B.1.1.529 in participants who are receiving mRNA-1273.529 (or mRNA-1273) as the 4th dose in Part 1 of this study.

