To evaluate the genetic and/or phenotypic relationships of isolated SARS-CoV-2 strains to the vaccine sequence	
 • Characterize the SARS-CoV-2 spike genetic sequence of viral isolates and compare with the vaccine sequence • Characterize the immune responses to vaccine breakthrough isolates

Abbreviations: AE = adverse event; AESI = adverse event of special interest; AR = adverse reaction; CDC = Centers for Disease Control and Prevention; GMFR = geometric mean fold rise; GMR = geometric mean titer ratio; GMT = geometric mean titer; MAAE = medically attended adverse event; mRNA = messenger ribonucleic acid; NP = nasopharyngeal; RT-PCR = reverse transcription polymerase chain reaction; SAE = serious adverse event; SARS-CoV-2 = severe acute respiratory syndrome coronavirus 2; SRR = seroresponse rate.

Table 4: Study Objectives and Endpoints for Part 2 (mRNA-1273.214 and mRNA-1273)

Objectives	Endpoints
Primary	
To demonstrate non-inferiority of the immune response of mRNA-1273.214 compared to mRNA-1273 booster administered as a 4 th dose against the B.1.1.529 strain at Day 29 or Month 3	
 Geometric mean titer (GMT) of mRNA-1273.214 and mRNA-1273 against the B.1.1.529 strain at Day 29 or Month 3 after study vaccine administration Ratio of $GMT_{mRNA-1273.214}/GMT_{mRNA-1273}$ against the B.1.1.529 strain at Day 29 or Month 3 after study vaccine administration
To demonstrate non-inferiority of the immune response of mRNA-1273.214 compared to mRNA-1273 booster administered as a 4 th dose against the prototype strain at Day 29 or Month 3	
 Geometric mean titer (GMT) of mRNA-1273.214 and mRNA-1273 against the prototype strain at Day 29 or Month 3 after study vaccine administration Ratio of $GMT_{mRNA-1273.214}/GMT_{mRNA-1273}$ against the prototype strain at Day 29 or Month 3 after study vaccine administration
To demonstrate superiority of the immune response of mRNA-1273.214 compared to mRNA-1273 booster administered as a 4 th dose against the B.1.1.529 strain at Day 29 or Month 3	
 GMT of mRNA-1273.529 and mRNA-1273 against the B.1.1.529 strain at Day 29 or Month 3 after study vaccine administration Ratio of $GMT_{mRNA-1273.529}/GMT_{mRNA-1273}$ against the B.1.1.529 strain at Day 29 or Month 3 after study vaccine administration

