An ANCOVA model will be carried out to assess the difference in immune response between mRNA-1273.214 and mRNA-1273 in the subgroup of participants who received the 4th dose. This analysis will be carried out for immune response against the B.1.1.529 strain and the prototype virus strain separately using the PPSI-Neg analysis population.

Specifically, for immune response against the B.1.1.529 strain, in the ANCOVA model, antibody titers at Day 29 post-booster against the B.1.1.529 strain will be a dependent variable, and a group variable (mRNA-1273.214 and mRNA-1273) will be the fixed effect, adjusting for age groups (< 65, ≥ 65 years) and pre-booster antibody titer level, if applicable. The GMT will be estimated by the geometric least square mean (GLSM) from the model and its corresponding 99% CIs will be provided for each group. The GMR (ratio of GMTs) for mRNA-1273.214 with respect to mRNA-1273 will be estimated by the ratio of GLSM from the model and the corresponding 99% CIs will be provided. The 99% CI for GMR will be used to assess the between group difference in immune response against the B.1.1.529 strain for mRNA-1273.214 at Day 29 compared to the mRNA-1273 as a booster for non-inferiority testing.

Against the B.1.1.529 strain, the non-inferiority of immune response of mRNA-1273.214 as compared to mRNA-1273 will be considered demonstrated if the lower bound of the corresponding 99% CI is ≥ 0.67 based on a non-inferiority margin of 1.5.

Once non-inferiority against B.1.1.529 is demonstrated, superiority of mRNA-1273.214 as compared to mRNA-1273 against B.1.1.529 will be tested (at Day 29); if the lower bound of the 99% CI of the GMR ratio is > 1 , superiority is demonstrated.

The same ANCOVA model will be used to assess immune response of mRNA-1273.214 against the B.1.1.529 strain at Month 3. The 96% CI for GMR will be used to assess the between group difference in immune response against the B.1.1.529 strain for non-inferiority and superiority. For the immune response against the prototype virus strain, the same analysis method will be used.

As part of the secondary analysis to assess for immune response against other variants, the same analysis method described above will be used. A 95% CI for GMR will be used to assess for non-inferiority and superiority.

Following section is applicable for both Part 1 and Part 2:

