2.1. Primary Objectives

2.1.1. Primary Immunogenicity Objective

Part 1

- To demonstrate non-inferiority of the immune response of mRNA-1273.529 compared to mRNA-1273 booster administered as a 4th dose against the B.1.1.529 strain at Day 29 or Month 3.

Part 2

- To demonstrate non-inferiority of the immune response of mRNA-1273.214 compared to mRNA-1273 booster administered as a 4th dose against the B.1.1.529 strain at Day 29 or Month 3.
- To demonstrate non-inferiority of the immune response of mRNA-1273.214 compared to mRNA-1273 booster administered as a 4th dose against the prototype strain at Day 29 or Month 3.
- To demonstrate superiority of the immune response of mRNA-1273.214 compared to mRNA-1273 booster administered as a 4th dose against the B.1.1.529 strain at Day 29 or Month 3.

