The same ANCOVA model will be used to assess immune response of mRNA-1273.214 against the B.1.1.529 strain at Month 3 (fourth and six primary hypotheses). The 96% CI for GMR will be used to assess the between group difference in immune response against the B.1.1.529 strain for non-inferiority and superiority. The same ANCOVA model, and the lower bound of the corresponding 96% CI that is ≥ 0.67 based on a non-inferiority margin of 1.5 will be used to demonstrate the non-inferiority for the immune response against the prototype virus strain at Month 3 (fifth primary hypothesis).

Part 2 of this study is considered to have met its primary objective if non-inferiority of mRNA-1273.214 against the B.1.1.529 strain, non-inferiority of mRNA-1273.214 against the prototype strain, and superiority of mRNA-1273.214 against the B.1.1.529 strain are demonstrated as compared to mRNA-1273 at Day 29 or Month 3.

Supportive analyses of the primary immunogenicity endpoints at Day 29 and Month 3 will also be performed in the PPSI. These analyses will be based on the ANCOVA model described above and will include pre-booster/baseline SARS-CoV-2 status (negative, positive, or missing) as a factor. The 99% CI for GMR will be used to assess differences between groups at Day 29 and the 96% CI for GMR at Month 3.

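### Part 2 has two incompatible rules for meeting its primary objective: non-inferiority alone, or non-inferiority plus superiority

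*Protocol*

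**What the plan says.** **The three-part rule.** The opening Part 2 paragraph of protocol 9.2 requires NI against both strains and "superiority of mRNA-1273.214 against the B.1.1.529 strain are demonstrated as compared to mRNA-1273 at Day 29 or Month 3". The synopsis gives this rule twice, under the hypotheses and under the immunogenicity analysis. SAP 4.2 repeats it. SAP 6.4.2.2.1, the operative analysis section, has only this rule, beginning "Part 2 of this study is considered to have met its primary objective if non-inferiority of mRNA-1273.214 against the B.1.1.529 strain".

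**The NI-only rule.** The paragraph on Day 29 testing in protocol 9.2 says "The primary immunogenicity objective is considered met if non-inferiority against the B.1.1.529 strain and the prototype strain are both demonstrated", and SAP 4.2 carries the same sentence. Superiority then follows as a later step, and Month 3 is to be handled in the same way.

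**The synopsis version of that sentence.** It reads "Non-inferiority against the B.1.1.529 strain and the prototype strain are both demonstrated if the lower bound". That defines when NI is shown and says nothing about the objective being met.

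**Where superiority sits.** It is one of the six primary hypotheses ("mRNA-1273.214, as a single booster dose, is superior to mRNA-1273 based on GMT ratio against the B.1.1.529 strain at Day 29", and again for Month 3). SAP 2.1.1 lists it as a primary immunogenicity objective: "To demonstrate superiority of the immune response of mRNA-1273.214 compared to mRNA-1273 booster administered as a 4th dose against the B.1.1.529 strain".

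**Two related passages.** Protocol 9.6.1 opens the superiority test without mentioning prototype: "Once non-inferiority against B.1.1.529 is demonstrated, superiority of mRNA-1273.214 as compared to mRNA-1273 against B.1.1.529 will be tested (at Day 29". Protocol Table 4 and the synopsis define the endpoint for the Part 2 superiority objective as "GMT of mRNA-1273.529 and mRNA-1273 against the B.1.1.529 strain at Day 29 or Month 3 after study vaccine administration".

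**The concern.** This is the decision rule for the confirmatory part of the trial. The two rules part company when both NI tests pass and superiority fails at both visits, which is a realistic result for a bivalent booster compared with an active control. The documents then support opposite conclusions, and either can be quoted in a report. A success criterion should not leave that choice open once the data are known.

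The two smaller faults concern the same objective. One is the order of testing: protocol 9.6.1 needs only B.1.1.529 NI before superiority, while protocol 9.2 and SAP 6.4.2.2.1 need NI on both strains. The other is the endpoint, which names a vaccine that neither Part 2 arm receives.

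**Working it through.** **1. The rules side by side**

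| Place | Condition for the Part 2 primary objective |
|---|---|
| Synopsis, hypotheses and immunogenicity analysis | NI B.1.1.529 + NI prototype + superiority |
| Protocol 9.2, opening Part 2 paragraph | NI + NI + superiority |
| Protocol 9.2, Day 29 testing paragraph | NI + NI |
| SAP 4.2, opening Part 2 paragraph | NI + NI + superiority |
| SAP 4.2, Day 29 testing paragraph | NI + NI |
| SAP 6.4.2.2.1 | NI + NI + superiority |

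The two sentences cannot refer to different objectives, because superiority is itself a primary hypothesis and a primary immunogenicity objective. SAP section 1 lets the SAP override the protocol, but the SAP contains both rules. SAP section 7 records no departure from the protocol.

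**2. Inputs**

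- From the documents: two-sided alpha 0.01 at Day 29 and 0.04 at Month 3; NI margin 1.5 (lower bound at least 0.67); superiority if the lower bound exceeds 1; 1328 fourth-dose participants per arm.
- Redacted, so assumed: SD of ln titre 1.0 to 1.5, and 350 to 1000 evaluable per arm (the plan allows analysis of a subset).

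**3. The plan's own figures**

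- Alpha: 0.01 + 0.04 = 0.05, as stated.
- Chance of at least one adverse event at 1% incidence: 1 − 0.99^1328 > 0.9999, consistent with the stated minimum of 90%.
- The Part 2 powers are redacted and cannot be reproduced.

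**4. A dataset on which the rules disagree**

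Take n = 1000 per arm, SD 1.5, and observed GMR 1.05 (B.1.1.529) and 1.00 (prototype) at both visits.

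- SE = SD × √(2/n) = 1.5 × √0.002 = 0.0671. The lower bound is exp(ln GMR − z × SE), with z = 2.576 (99%) or 2.054 (96%).
- B.1.1.529: 0.883 at Day 29, 0.915 at Month 3.
- Prototype: 0.841 at Day 29, 0.871 at Month 3.

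All four bounds are at least 0.67, so the NI-only rule is met. Neither B.1.1.529 bound exceeds 1, so the three-part rule is not.

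**5. How often each rule is met**

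NI power = Φ((ln GMR + ln 1.5)/SE − z). Superiority power = Φ(ln GMR/SE − z). Joint NI for the two strains is bounded below by the sum of the two powers minus 1.

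- *GMR 1.0 for both strains, SD 1.5, n = 350, Day 29.* SE = 0.1134; Φ(0.4055/0.1134 − 2.576) = Φ(1.00) = 0.841; joint NI at least 2 × 0.841 − 1 = 0.68. With the rounded limit 0.67 in place of 1/1.5 this becomes 0.66. At n = 1000 it is about 1.00.
- *Three-part rule at GMR 1.0.* At most 0.005 + 0.02 = 0.025.
- *B.1.1.529 GMR 1.1, SD 1.5, n = 1000.* NI about 100%. Superiority is Φ(0.0953/0.0671 − 2.576) = 12% at Day 29 and Φ(0.0953/0.0671 − 2.054) = 26% at Month 3.

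**6. Probability that the rules disagree**

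This comes from a normal-approximation simulation with 300,000 replicates per scenario. The NI-only rule was allowed at either visit. Assumed: n = 500, 1000 or 1328; SD 1.0 or 1.5; prototype GMR 1.0; correlation 0.5 between strains and 0 or 0.8 between visits.

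| True B.1.1.529 GMR | Rules disagree |
|---|---|
| 1.0 | 96% to 98% |
| 1.1 | 19% to 83% |
| 1.2 | under 0.1% to 51% |

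**The case against.** The strongest reply is that the rules are not evenly matched. The three-part rule appears five times, including in the SAP's operative section, and superiority is labelled primary throughout, even in the rows of protocol Table 10. The NI-only sentence is one sentence in a description of steps, matching the Part 1 wording, where NI alone is the right criterion. It is most plausibly a drafting slip, and an NI-only claim would contradict the rest of the plan. All of this is fair, and it shows which way to correct the text. It does not remove a sentence that says in terms that the objective is met, in both documents. There are other traces of the NI-only usage: protocol 9.3 and SAP 4.3 attach the label of primary objective at Month 3 to a power figure given separately from superiority, and the Table 10 title refers to key secondary objectives, which Part 2 does not have.

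The second reply is that the illustration depends on assumptions and can be made milder. That stands. At GMR 1.1, n = 1000 and SD 1.0, superiority power is about 33% (Day 29) and 53% (Month 3). At GMR 1.2 and n = 1000, Month 3 power is about 98% (SD 1.0) or 75% (SD 1.5). The planned GMRs are redacted, so how likely the sponsor thought the discordant result cannot be judged. The testing-strategy figure is also not visible, though it could not cancel the sentence.

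The third reply is that the two related faults are minor. That also stands. The SAP requires NI on both strains before superiority, and the three-part rule needs prototype NI in any case. The vaccine name is an evident slip, since the objective in the same row names mRNA-1273.214.

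**Conclusion.** The concern holds. Protocol 9.2 and SAP 4.2 each contain two success rules for Part 2 that give opposite answers when both NI tests pass and superiority fails at both visits. This follows from the text alone. The conflict runs one way: any result that satisfies the three-part rule also passes both NI tests at that visit.

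Its practical size depends on the true effect. With no advantage over mRNA-1273 the rules almost always disagree; with a GMR of 1.2 the range is from almost never to about half the time. Those figures rest on assumed SDs, sample sizes and correlations. Neither reading breaks the 0.05 family-wise alpha, provided superiority itself is claimed only when tested as planned. The correction is required because the ambiguity lies in a confirmatory success criterion. The superiority gate and the endpoint label are lesser errors that belong in the same correction.

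**What to change.** 1. In the Day 29 testing paragraph of protocol 9.2 and of SAP 4.2, replace the statement that the primary immunogenicity objective is met with the synopsis form, which begins "Non-inferiority against the B.1.1.529 strain and the prototype strain are both demonstrated if the lower bound". The three-part rule then stands as the only success criterion for Part 2.
2. In protocol 9.6.1 and the matching synopsis analysis text, open the superiority test only after NI is shown for both B.1.1.529 and prototype at that visit.
3. In protocol Table 4 and the synopsis, change mRNA-1273.529 to mRNA-1273.214 in the two endpoints of the Part 2 superiority objective.

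Date the correction and state whether Day 29 or Month 3 results had been unblinded by then. The cost is a few sentences of wording in the two documents. The alpha split stays at 0.01 + 0.04, and no new data or analysis is needed.
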